16 ADMINISTRATIVE PROCEDURES

16.1 Regulatory and Ethical Compliance

This clinical trial will be conducted in accordance with the principles of the Declaration of Helsinki, and in compliance with ISO 14155:2011 Clinical investigation of medical devices for human subjects – Good clinical practice, Code of Federal Regulations (CFR), and laws and regulations of foreign countries, whichever affords greater protection to subjects. The

trial shall also be conducted in accordance with the Sponsor's Standard Operating Procedures (SOPs) and all other applicable regulations. The Investigator and all clinical trial staff will conduct the clinical trial in compliance with this protocol. The Investigator will ensure that

all personnel involved in the conduct of the clinical trial are qualified to perform their assigned duties through relevant education, training, and experience.

16.2 Informed Consent Procedures

Voluntary informed consent will be obtained from every subject prior to the initiation of any screening or other clinical trial-related procedures. The Investigator must have a defined process for obtaining consent. Specifically, the Investigator, or designee, will explain the clinical trial to each potential subject and the subject must indicate voluntary consent by signing and dating the approved informed consent form. The subject must be provided an opportunity to ask questions of the Investigator, and if required by local regulation, other qualified personnel. The Investigator must provide the subject with a copy of the consent form written in a language the subject understands. The consent document must meet all applicable local laws and will provide subjects with information regarding the purpose, procedures, requirements, and restrictions of the clinical trial, along with any known risks

and potential benefits associated with the investigational product, the available compensation, and the established provisions for maintaining confidentiality of personal, protected health information. Subjects will be told about the voluntary nature of participation in the clinical trial and will be provided with contact information for the appropriate individuals should questions or concerns arise during the clinical trial. The subject also will be told that their records may be accessed by appropriate authorities and Sponsor-designated personnel. The Investigator must keep the original, signed copy of the consent and must provide a duplicate copy to each subject.

16.3 Responsibilities of the Investigator and IRB/IEC

Before clinical trial initiation, this protocol, the informed consent form (and assent form, if applicable), any other written information provided to subject, and any advertisements planned for subject recruitment must be approved by an Institutional Review Board / Independent Ethics Committee (IRB/IEC). A master list of IRBs/IECs for this clinical trial can be found in the Trial

Master File. The Investigator must provide documentation of IRB/IEC approval to the Sponsor. The approval must be dated and must identify the applicable protocol, amendments (if any), informed consent form, assent form (if any), all applicable recruiting materials, written information for subjects, and subject compensation programs. The IRB/IEC must be provided with a copy of the Investigator's Brochure, any periodic safety updates, and all other information as required by local regulation and/or the IRB/IEC. At the end of the clinical trial or in the case of early termination, the Investigator will notify the IRB/IEC of the clinical trial's final status. Finally, the Investigator will report to the IRB/IEC on the progress of the clinical trial at intervals stipulated by the IRB/IEC.

16.3.1 Sponsor and Monitoring Responsibilities

The Sponsor will designate a monitor to conduct the appropriate site visits at the appropriate intervals. The clinical investigation will be monitored, following the Protocol Monitoring Plan, to ensure that: the rights and well-being of the subjects are protected; the reported data are accurate, complete, and verifiable from the source documents; the equipment used to assess variables in the clinical investigation is maintained and calibrated per manufacturer instructions and Sponsor requirements; the study is conducted in compliance with the current approved protocol (and amendment[s], if applicable), with current Good Clinical Practice (GCP), and with applicable regulatory requirements.

All investigative sites will have a site initiation. Monitoring will be conducted periodically while the clinical study is ongoing. Monitoring methods may include site visits, telephone, written and fax correspondence. The assigned CSM will contact each site at appropriate intervals. The Lead Clinical Site Manager (LCSM) will determine the frequency of site visits. Closeout visits will take place after the last visit of the last subject.

16.4 Regulatory Documentation and Records Retention

Essential documents must be retained by the investigator in compliance with the medical device directive and its local transposition as well as other applicable national and international regulations. The Investigator(s)/institution(s) must comply with record retention stipulations outlined in the Clinical Study Agreement. Additionally the Investigator will be supplied with further instruction at study completion.

16.5 Clinical Trial Results

The Investigator will notify the accredited ethics committee of the end of the study as required by the ethics committee. The end of the study is defined as database lock. In case the study is ended prematurely, the Investigator will notify the accredited ethics committee, including the reasons for the premature termination. Within 1 year after the end of the study, the Investigator/sponsor will

submit a final study report with the results of the study, including any publications/abstracts of the study, to the accredited ethics committee as required.

Short Title:**Statistical Analysis Plan****ILH297-C001 /****NCT03280108****Full Title:****Statistical Analysis Plan****ILH297-C001**

Protocol Title: Clinical Investigation of AcrySof® PanOptix™ IOL Model
TFNT00

Project Number: A10875

Protocol TDOC Number: TDOC-0053702

Author: [REDACTED]

[REDACTED]

Approvals: See last page for electronic approvals.

Job Notes:

This is the second revision (Version 3.0) Statistical Analysis Plan for this study. This version of the Statistical Analysis Plan is based on Version 4.0 of the study protocol. At the time of revision, 250 subjects enrolled in this study.

[REDACTED]

Executive Summary:

Key Objectives:

The objective of this study is to compare the visual outcomes of the AcrySof PanOptix IOL Model TFNT00 to that of the AcrySof Monofocal IOL Model SN60AT.

The primary effectiveness objectives are to demonstrate comparable distance vision (4 m), as well as superior near vision (40 cm), of the AcrySof PanOptix IOL Model TFNT00 compared to the AcrySof Monofocal IOL Model SN60AT. Secondary effectiveness objectives are to demonstrate superiority of the AcrySof PanOptix IOL Model TFNT00 compared to the AcrySof Monofocal IOL Model SN60AT, in intermediate vision (66 cm) and in the overall need to wear eyeglasses to see.

The primary safety objectives are to estimate the cumulative rate of secondary surgical interventions related to the optical properties of the IOL and to evaluate the mean contrast sensitivity with and without glare for mesopic and photopic conditions. The secondary safety objective is to estimate the rates of severe and most bothersome visual disturbances as reported by the subject using a questionnaire. The third safety objective is to estimate rates of cumulative and persistent Adverse Events in first eyes in comparison to IS EN ISO 11979-7:2014 Safety and Performance Endpoint Rates.

Decision Criteria for Study Success:

Primary effectiveness will be considered supported if AcrySof PanOptix IOL Model TFNT00 demonstrates non-inferior distance vision and superior near vision when compared to the AcrySof Monofocal IOL Model SN60AT.

The non-inferiority hypothesis will be considered supported if the upper 95% confidence limit on the difference between the two groups is less than the non-inferiority margin of 0.10 logMAR.

The superiority hypothesis will be considered supported if the upper 97.5% confidence limit on the difference between the two groups is less than 0.0 logMAR.

Table of Contents

1.1 Study Objectives

Effectiveness Objectives

The co-primary effectiveness objectives are to:

- Demonstrate non-inferiority of AcrySof IQ PanOptix IOL Model TFNT00 compared to the concurrent control AcrySof Monofocal IOL Model SN60AT in mean photopic monocular best corrected distance visual acuity (4 m) for the first operative eye at month 6 (Visit 4A).
- Demonstrate superiority of AcrySof IQ PanOptix IOL Model TFNT00 compared to the concurrent control AcrySof Monofocal IOL Model SN60AT in mean photopic monocular distance corrected visual acuity at near (40 cm) for the first operative eye at month 6 (Visit 4A).

The secondary effectiveness objectives are to:

- First secondary: Demonstrate superiority of AcrySof IQ PanOptix IOL Model TFNT00 compared to the concurrent control AcrySof Monofocal IOL Model SN60AT in mean photopic monocular distance corrected visual acuity at intermediate (66 cm) for the first operative eye at month 6 (Visit 4A).
- Second secondary: Demonstrate superiority of AcrySof IQ PanOptix IOL Model TFNT00 compared to the concurrent control AcrySof Monofocal IOL Model SN60AT in proportion of subjects who respond “Never” to Q1 of the IOLSAT questionnaire (Overall, in the past 7 days, how often did you need to wear eyeglasses to see?) at month 6 (Visit 4A).

Safety Objectives

The co-primary safety objectives are to:

- Estimate the cumulative rate of secondary surgical interventions (SSIs) related to the optical properties of the IOL for first operative eye up to month 6 (Visit 4A).
- Evaluate the mean binocular contrast sensitivity with and without glare for photopic and mesopic conditions at month 6 (Visit 4A).

The secondary safety objective is to:

- Estimate rates of severe and most bothersome (separately) visual disturbances as reported by the subjects using a questionnaire (QUVID) at month 6 (Visit 4A).

The third safety objective is to:

- Evaluate rates of cumulative and persistent Adverse Events in first eyes at 6 months (Visit 4A) in comparison to IS EN ISO 11979-7:2014 Safety and Performance Endpoint grid rates.

1.2 Study Description

This study is a prospective, multi-center, non-randomized, vision assessor-masked, parallel group confirmatory trial. It compares an investigational trifocal IOL and a commercially available monofocal IOL. Approximately 125 subjects will be implanted bilaterally with the investigational lens and approximately 125 subjects will be implanted bilaterally with the control lens. Potential subjects will be screened for enrollment into the trial. Those qualifying will attend a total of 10 visits (7 visits occur postoperatively) over a 7 month period.

An overview of the study design is depicted in Table 1-1.

The schedule of visits is presented in Section 6 of the protocol.

Table 1-1 **Study Design**

Time From Implantation	1st Eye	2nd Eye
-30 to 0 days pre-operatively	Visit 0 (monocular [1st and 2nd eye] and binocular)	
Operative (IOL implantation)	Visit 00	Visit 00A*
1 - 2 days post-operatively	Visit 1 (monocular)	Visit 1A (monocular)
7 - 14 days post-operatively	Visit 2 (monocular)	Visit 2A (monocular)
30 - 60 days post-operatively	Visit 3 (monocular)	Visit 3A (monocular)
120 - 180 days post-operatively (after 2nd eye implantation)	Visit 4A** (monocular [1st and 2nd eye] and binocular)	

*NOTE: IOL implantation in the second eye is intended to occur between 7 and 30 days after IOL implantation in the first eye.

1.3 Randomization

Not applicable. This is a non-randomized study.

1.4 Masking

Site personnel performing [REDACTED] all visual acuity assessments [REDACTED] [REDACTED] and all contrast sensitivity assessments will be masked with regard to treatment assignment until after the final database lock (Visit 4A). The surgeons and subjects will not be masked in this study.

1.5 Interim Analysis

No interim analyses are planned for this study.

2 Analysis Sets

All monocular measures from eyes implanted with a non-study lens and binocular measures assessed in subjects with at least one non-study IOL implant will be excluded from all analysis sets. Treatment assignments for final analysis will be based on the lens implanted.

Although all sites are expected to contribute both test and control subjects, due to the non-randomized nature of the study it is possible that a site may enroll all subjects in one group. Such sites, and possibly additional sites with low enrollment, will be combined into one pseudo site to ensure that at least two subjects are in each IOL group to avoid estimation issues with the use of mixed effects models. Sites will not be combined for all other descriptive effectiveness and safety summaries

2.1 Effectiveness Analysis Sets

The All-Implanted Analysis Set (AAS) includes all eyes with successful IOL implantation with at least one post-operative visit and will be the primary analysis set for all effectiveness analyses except [REDACTED] [REDACTED]

The Best-Case Analysis Set (BAS) will be the primary analysis set for [REDACTED] and contrast sensitivity, and includes all eyes successfully implanted that had:

- at least 1 post-operative visit;
- no preoperative ocular pathology;
- no macular degeneration detected at any time; and
- no major protocol deviations.

2.2 Safety Analysis Set

The Safety Analysis Set (SAS) will include all eyes with attempted IOL implantation (successful or aborted after contact with the eye). The SAS will be the primary set for all safety analyses except contrast sensitivity.

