	
• Second secondary: Demonstrate superiority of AcrySof IQ PanOptix IOL Model TFNT00 compared to the concurrent control AcrySof Monofocal IOL Model SN60AT in proportion of subjects who respond "Never" to Q1 of the IOLSAT questionnaire (Overall, in the past 7 days, how often did you need to wear eyeglasses to see?) at Month 6 (Visit 4A). 
Safety:
 
The co-primary safety objectives are to
 
• Estimate the cumulative rate of secondary surgical interventions (SSIs) related to the optical properties of the IOL for the first operative eye up to Month 6 (Visit 4A).• Evaluate the mean binocular contrast sensitivity with and without glare for photopic and mesopic conditions at Month 6 (Visit 4A). 
The secondary safety objective is to estimate rates of severe and most bothersome (separately) visual disturbances as reported by the subjects using a questionnaire (QUVID) at Month 6 (Visit 4A).
 
The third safety objective is to evaluate rates of cumulative and persistent Adverse Events in first operative eyes at Month 6 (Visit 4A) in comparison to ISO 11979-7 Safety and Performance Endpoint (SPE) grid rates.

Clinical Trial Design:	This study is a prospective, multicenter, non-randomized, vision assessor-masked, parallel-group confirmatory trial.
No. of Subjects:	
Required: 113 subjects bilaterally implanted with the AcrySof IQ PanOptix IOL Model TFNT00 and 113 subjects bilaterally implanted with the concurrent control AcrySof Monofocal IOL Model SN60AT.
 
Planned: Approximately 125 subjects bilaterally implanted with the AcrySof IQ PanOptix IOL Model TFNT00 and 125 subjects bilaterally implanted with the concurrent control AcrySof Monofocal IOL Model SN60AT to achieve the required numbers assuming a dropout rate of 10%, approximately, at 6 months post implantation.

Region(s):	United States
Clinical Trial Duration:	
a. Total expected duration of the clinical investigation: 13 monthsb. Expected duration of each subject's participation: ~7 monthsc. Planned follow up duration: 6-months post second eye implantationd. Estimated time needed to select the number of subjects (ie, enrollment period): 6 months

Clinical Trial Population:	Adults subjects, 22 years of age or older, who require bilateral cataract extraction.	
Treatments:	Test Article:	AcrySof IQ PanOptix IOL Model TFNT00

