13.1 General Information

An AE is any untoward medical occurrence, unintended disease or injury, or untoward clinical signs (including abnormal laboratory findings) in subjects, users, or other persons, whether or not related to the investigational medical device (test article). Refer to the Glossary of Terms and figures below for categories of AEs and SAEs.

Figure 13–1 Categorization of All Adverse Events

[figure not shown]
[figure not shown]

Figure 13-2

Categorization of All Serious Adverse Events

Specific Events Relevant to this Protocol

In addition to reporting all AEs (serious and non-serious) meeting the definitions, the Investigator must report any occurrence of the following as an SAE:

[figure not shown]
Cumulative Serious Adverse Events

- Cystoid macular edema
- Hypopyon
- Endophthalmitis
- Lens dislocation from posterior chamber
- Pupillary block
- Retinal detachment
- Secondary surgical intervention (excluding posterior capsulotomy)

Peristent Serious Adverse Events

- Corneal stromal edema
- Cystoid macular edema
- Iritis
- Raised IOP requiring treatment

This list is consistent with the categories provided in ISO 11979-7 SPE grid rates. A persistent AE is an AE that is present at the conclusion of a clinical investigation per ISO 11979-1 terms and definitions. Any other potentially sight-threatening event may also be considered serious based on the judgment of the Investigator and should be reported appropriately as delineated in Section 13.3 Procedures for Recording and Reporting Deficiencies.

Secondary Surgical Interventions (SSI)

Secondary Surgical Interventions reporting will be sub-categorized using the following terminology: exchange, removal, and repositioning. Indications and associated definitions for these outcomes are provided in Section 18 Appendices, Table 18-2.

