5.3 Statistical Methods for Safety Analyses

Except otherwise stated, the analysis set for all safety analyses is the safety analysis set as defined in Section 2.2. Baseline will be defined as the last measurement prior to exposure to investigational product, except otherwise stated.

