5.3.4 Adverse Events

The third safety endpoint is adverse events. Incidence rates observed for each IOL group will be compared to the cumulative and persistent adverse event Safety and Performance Endpoint rates in IS EN ISO 11979-7:2014. An eye with multiple ocular adverse events of the same preferred term is only counted once toward the total of this preferred term. The Safety and Performance Endpoint rate is considered not exceeded if the lower exact binomial 95% confidence limit does not exceed the Safety and Performance Endpoint rate.

The following SAS pseudo code will be used to generate the summaries above.

```
proc freq data=AE_SPE;
by SPE_AE;
tables LENS_MODEL / binomial (exact) alpha=0.05;
run;
```

The frequencies of adverse events will be presented overall, and by subcategories of age (<65 years vs. \geq 65 years) and investigative site, separately for cumulative and persistent adverse events. Additionally, frequencies and 95% (two-sided) exact confidence intervals will be reported for adverse events related to the IOL for each IOL group. Adverse events related to the IOL are referred to as adverse device effects.

Adverse events will be summarized in the following tables, by IOL group:

1. All Adverse Events (Serious and Non-Serious Combined)
 - a. Ocular
 - b. Non-Ocular
2. All Adverse Device Effects
 - a. Ocular
 - b. Non-Ocular
3. All Serious Adverse Events (including Serious Adverse Device Effects)
 - a. Ocular
 - b. Non-Ocular
4. Subject Listings
 - a. Non-Serious Ocular
 - b. Non-Serious Non-Ocular
 - c. Serious Ocular
 - d. Serious Non-Ocular

All ocular tables will be presented separately for first operative eyes and all eyes.

In addition, listings of adverse events will be provided. The listings will include the following variables: treatment, site, subject, eye, days from surgery, duration, adverse event description, causality, severity, seriousness, outcome and preferred term.

Table 5-2**Adverse Event Safety and Performance Endpoint Rates**

Adverse Event	SPE Rate (%)
Cumulative	
Cystoid Macular Oedema	3.0
Hypopyon	0.3

Endophthalmitis ^a	0.1
Lens dislocated from posterior chamber	0.1
Pupillary block	0.1
Retinal detachment	0.3
Secondary surgical intervention ^b	0.8
Persistent	
Corneal stroma oedema	0.3
Cystoid macular oedema	0.5
Iritis	0.3
Raised IOP requiring treatment	0.4

^a Endophthalmitis is defined as inflammatory reaction (sterile or infectious) involving the vitreous body.

^b Excludes posterior capsulotomies.

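### Persistent adverse event rates default to the Safety Analysis Set, so eyes with no Month 6 examination stay in the denominator and pull the SPE comparison toward "not exceeded"

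*SAP*

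**What the plan says.** The analysis set is fixed in two places. SAP 2.2 defines it: "The Safety Analysis Set (SAS) will include all eyes with attempted IOL implantation (successful or aborted after contact with the eye"). It then applies it: "The SAS will be the primary set for all safety analyses except contrast sensitivity". SAP 5.3 repeats the default: "Except otherwise stated, the analysis set for all safety analyses is the safety analysis set as defined in Section 2.2". SAP 5.3.4, which holds the SPE comparison, names no other set and gives no denominator for persistent events.

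The endpoint is tied to the end of the study. Protocol 13.1 says: "A persistent AE is an AE that is present at the conclusion of a clinical investigation per ISO 11979-1 terms and definitions". The third safety objective in SAP 1.1 is: "Evaluate rates of cumulative and persistent Adverse Events in first eyes at 6 months (Visit 4A"), compared with the ISO SPE rates. By the rule in SAP 5.3.4, an SPE rate is "considered not exceeded if the lower exact binomial 95% confidence limit does not exceed the Safety and Performance Endpoint rate".

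The Protocol synopsis plans about 125 subjects per arm "to achieve the required numbers assuming a dropout rate of 10%, approximately, at 6 months post implantation"; the required number is 113. The missing-data sensitivity analyses (Protocol section on handling of missing data, SAP 4.5) cover the co-primary effectiveness endpoints and contrast sensitivity, not adverse events.

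**The concern.** A denominator of attempted eyes suits the cumulative categories, where an event at any time counts. It does not suit the four persistent ones: corneal stromal oedema, cystoid macular oedema (CME), iritis and raised IOP requiring treatment. The Month 6 slit lamp, tonometry and dilated fundus examinations fall in Part 2 of Visit 4A (Protocol 12.2.5). An eye that misses them, with no event reported, adds one to the denominator and can add nothing to the numerator.

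The error runs one way: the estimated rate falls and the comparison leans toward "not exceeded", more so in the arm that loses more eyes. The SPE rates are small (0.3% to 0.5%) and each arm has little more than 100 first eyes, so verdicts turn on two or three events and a modest change of denominator can matter. No planned sensitivity analysis would show it.

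**Working it through.** **Inputs.** Planned first eyes per arm: 125 (SAP 1.2). Completers: 113 (SAP 7). Persistent SPE rates (SAP Table 5-2): corneal stromal oedema 0.3%, iritis 0.3%, raised IOP 0.4%, CME 0.5%. Sidedness: the Protocol synopsis calls the SPE calculation 1-sided; the SAP 5.3.4 code requests an exact interval with alpha 0.05, which is a two-sided 95% interval with 2.5% in the lower tail. Both readings are carried through.

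**The plan's own figure.** SAP 7 says that 0 events in 113 eyes gives an upper exact 95% limit below 3%. The upper limit is 1 − a^(1/113). With a = 0.05 it is 2.62%, which reproduces the statement; with a = 0.025 it is 3.21%, which does not. The precision statement therefore uses a one-sided limit, and the completer number rather than 125.

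**Dilution.** If x events are seen and the missing eyes contribute none, (x/125) ÷ (x/113) = 113/125 = 0.904, a relative reduction of 9.6%.

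**Effect on the verdict.** The exact lower limit L for x events in n eyes solves P(X ≥ x | n, L) = a, so L is the a-quantile of a Beta(x, n − x + 1) distribution. The SPE is exceeded when L is above it.

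- One-sided 95% (a = 0.05), x = 2: L = 0.285% at n = 125, 0.299% at 119, 0.302% at 118 and 0.315% at 113. Against 0.3% the verdict changes between 119 and 118 eyes, that is with 7 of 125 eyes unexamined (5.6%).
- Two-sided 95% (a = 0.025), x = 3: L = 0.498% at n = 125, 0.502% at 124 and 0.551% at 113. Against 0.5% one unexamined eye is enough.

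Fewest events that exceed each persistent SPE, first eyes:

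| SPE | One-sided, n = 125 / 113 | Two-sided, n = 125 / 113 |
|---|---|---|
| 0.3% (corneal stromal oedema, iritis) | 3 / 2, changes | 3 / 3 |
| 0.4% (raised IOP) | 3 / 3 | 3 / 3 |
| 0.5% (CME) | 3 / 3 | 4 / 3, changes |

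**All eyes.** With 250 against 226 eyes no persistent verdict changes under either reading. The thresholds at both sizes are 3, 4 and 4 events one-sided, and 4, 4 and 5 two-sided, for 0.3%, 0.4% and 0.5%.

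**How likely a boundary count is.** With 113 eyes and a true rate equal to the SPE, the binomial probability of exactly 2 events at 0.3% is about 4%, and of exactly 3 at 0.5% about 1.7%. At an assumed true rate of 1%, exactly 2 events has probability about 21%.

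**The case against.** The best reply is that membership of an analysis set is not the same as being in a denominator. The All-Implanted set needs only one postoperative visit, yet the primary model uses Visit 4A records without imputation. Month 6 questionnaire rates also fall under the Safety Analysis Set, and a subject who never answered has no response to count. The precision statement uses 113 eyes, and the SAP 5.3.4 code tabulates lens model rather than an event indicator, so it does not settle the matter. This stands in part: a reader might infer that the plan declares unexamined eyes event-free, and no sentence does. But an adverse event with no report leaves no missing value to drop. Under the stated default such an eye stays in as a non-event unless an exception is written, and none is.

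Second, early leavers are not wholly unobserved. Protocol 12.3 calls for Early Exit procedures when a subject is discontinued at an unscheduled visit. The persistent categories are reportable as serious events, and events ongoing at exit are followed up to database lock (Protocol 13.6). This stands, and is why the dilution is "up to" 9.6%. The documents do not say, however, whether an event ongoing at exit counts as persistent.

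Third, the change of verdict is a boundary effect of a discrete test, and which category it touches depends on the sidedness. That is correct. A reader might infer that 10% dropout will overturn an SPE finding; the calculations show only that it can, at two specific counts.

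Fourth, this is the third safety objective. The SAP's success criteria are effectiveness only, and its accountability table and event listings should allow a rate on examined eyes to be recomputed. This limits the consequence but does not supply a prespecified denominator.

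**Conclusion.** The concern holds in a limited form. The stated default, not silence alone, puts first eyes without a Visit 4A examination into the denominator of a rate defined at study conclusion. At the planned dropout this lowers each persistent rate by up to 9.6% relative, always toward "not exceeded". It decides a first-eye verdict only at exactly 2 events against the 0.3% SPE (one-sided limit) or exactly 3 persistent CME events against 0.5% (two-sided interval). It does not do so for raised IOP, or for all eyes, between the planned denominators.

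This rests on three assumptions: about 125 attempted and 113 examined first eyes in the arm; no persistent event counted among the eyes not examined; and a literal reading of SAP 2.2 and 5.3. The change should be made because it is nearly free and concerns a prespecified comparison with a standard. It does not touch the effectiveness conclusions.

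**What to change.** Add to SAP 5.3.4: for the four persistent categories, the primary denominator is first operative eyes with the relevant examination at Visit 4A. Early leavers should not be added to it because of their outcome. Bringing in those with an unresolved event while leaving out those examined and event-free at exit would select on the outcome and push the rate up.

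Report two sensitivity analyses: (a) Visit 4A eyes plus every early leaver with an exit examination, with or without the event, using status at exit; and (b) the full Safety Analysis Set. Keep the Safety Analysis Set for the cumulative categories. State in the same place whether the 95% limit is one-sided or two-sided, since that determines which verdict is sensitive.

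The cost is a few SAP sentences and one or two extra table rows, with no new data. Persistent rates will look slightly less favourable. The primary rate will also assume that examined eyes represent those not examined, which the two sensitivity rows help a reader to judge.
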